10.3.7. Conclusion on non-inferiority effectiveness

In accordance with EMA recommendations for clinical studies of immunoglobulin normal for intravenous administration (*Guideline on the clinical investigation of human normal immunoglobulin for intravenous administration (IVIg)*, *EMA/CHMP/BPWP/94033/2007 rev. 4, 16 December 2021)* the obtained results will be compared with literature data The conclusion of non-inferiority of the drug Bioven, solution for infusions 10%, in the treatment of chronic immune thrombocytopenia, will be made according to the main efficacy variable using an approach based on confidence intervals. To do this, the calculated limits of the 95% confidence interval (CI) for the difference in the

percentage of positive results according to the main variable ("the drug is effective") for the studied group must be compared with the limit of the non-inferiority zone - effectiveness that is not inferior (-25%) to the calculated based on data for comparison. If the lower limit of the CI is greater than the

| Bioven | Page 74 |
|----------------------------|--------------------------------|
| Trial Code: 2021-BV-ITP-BP | Version 1.4 from July 03, 2023 |

lower limit of the non-inferiority zone (non-inferiority), then it will be considered that the study drug is not inferior in effectiveness compared to literature data.

10.4. Data set for analysis

ITT (Intention-to-treat population) - all study participants who took the study drug at least once. Data from this sample will be used for safety analysis.

PP (Per Protocol) - all patients who met the requirements of the protocol. This population includes all patients who received protocol therapy in full, completed all scheduled visits, and had no significant protocol deviations. The data obtained on this sample will be used for analysis according to the criteria of drug effectiveness.

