5th visit (Day +21 \pm 3 days) – physical examination, assessment of the status of hemorrhagic syndrome, blood sampling to determine platelet count, manual platelet counts, biochemical blood test, Coombs test in case hemolysis was detected during the previous visit (according to the laboratory data).

If a decrease of platelets count $< 30 \times 10^9/L$ was recorded, then approximately a day after the visit, an additional blood test is performed with a platelet count.

This visit can be performed by telephone / video, provided that the patient's status can be adequately assessed and biomaterials for laboratory tests can be sampled in Local Laboratory or at the collection point of the Central Laboratory designated by the Sponsor;

6th visit (Day +28 + 1-3 days) – physical examination, assessment of the status of the hemorrhagic syndrome, blood sampling to determine platelet count, manual platelet counts, biochemical blood test, Coombs test, Total IgG levels (g/l).

If a decrease of platelets count $< 30 \times 10^9/L$ was recorded, then approximately a day after the visit, an additional blood test is performed with a platelet count.

This is a face-to-face visit. Completion of the study.

Statistical analysis:

Populations for statistical analysis:

ITT (Intention-to-treat population) – all participants of the study who have taken the study drug at least once. The data obtained from this sample will be used for safety analysis.

PP (Per Protocol) – all patients who have met the requirements of the protocol. This population includes all patients who received the protocol-prescribed therapy in full, who completed all the prescribed visits and did not have significant deviations from the protocol. The data obtained from this sample will be used for analysis based on efficacy criteria.

Sample size calculation.

Statistical analysis of endpoints will be descriptive with testing of the null hypothesis (non-inferiority study).

In accordance with the EU recommendations on the clinical investigation of human normal immunoglobulin for intravenous administration (*Guideline on the clinical investigation of human normal immunoglobulin for intravenous administration (IVIg), EMA/CHMP/BPWP/94033/2007 rev. 4, 16 Dec 2021*) the obtained results will be compared with literature data.

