- Patient's wish
- Occurrence of severe and/or unexpected AE/AR in patient during the study, that require discontinuation of the drug;
- The need to prescribe drugs prohibited in this study.
- Significant deterioration of the patient's condition during the study period;
- Failure of the patient to adhere to the treatment regimen;
- Failure of the patient to follow the procedures established under the protocol;

Due to the variability of PLT levels in patients with chronic immune thrombocytopenia (wave), it is possible to re-screen or extend the duration of the screening phase, but only if the subject meets all other specified inclusion criteria and has no inclusion or exclusion criteria.

Patients who drop out at the screening stage are not included in the efficacy and safety analysis, as they do not receive any doses of the investigational drug (ID).

Patients who do not receive a full course of study drug are included in the safety analysis but not in the efficacy analysis.

Patients who dropped out of the study after completion of SD administration during the followup period are considered in the efficacy and safety analysis. The data of such patients are evaluated by parameters that can be analyzed at a certain point in time. The dropped data are not analyzed.

For all patients who complete the study due to AE, requiring discontinuation of treatment with the studied drugs, it is necessary to conduct the procedures of the final visit in the near future after the development of AE. After stopping treatment, the patient should be monitored until the reaction disappears or its clinically significant signs. Patients who received at least 1 dose of SD but prematurely dropped out of the study are included by the investigator in the analysis of tolerability of the study drug.

The reasons for premature withdrawal from the study are indicated in the Individual registration form.

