10 STATISTICS

10.1 Content of statistical analysis

The null hypothesis for the primary efficacy endpoint H0: $p-p_0 \leq \delta$, where clinical effectiveness p is the proportion of patients who responded to therapy with the study drug BIOVEN; p_0 - proportion of patients responding to therapy according to literature data: δ - the limit of the difference of proportions without clinical significance. An alternative hypothesis H1: $p-p_0 > \delta$ («non-inferiority study» according to the guideline EMA «Points to consider on switching between superiority and non-inferiority» CPMP/EWP/482/99, London, 27 July 2000 Ta EMA "ICH Topic E 9 Statistical Principles for Clinical Trials" CPMP/ICH/363/96).

According to the EU recommendations on clinical studies of immunoglobulin normal for intravenous administration (Guideline on the clinical investigation of human normal immunoglobulin for intravenous administration (IVIg), EMA/CHMP/BPWP/94033/2007 rev. 3, 28 June 2018) the obtained results will be compared with literature data.

To test the null hypothesis, a two-tailed test will be used, based on the principles of estimating a 95% confidence interval for the difference in proportions and comparing it with the lower limit of equivalence (at a significance level of α 5%). For non-inferiority research, the null hypothesis is rejected if the conditions are met:

$$\sqrt{n(p-p_0-\delta) / p^{(1-p^{-})} > z_{\alpha/2}}$$

or
 $(p-p_0-\delta) / \sqrt{(\frac{p(1-p)}{n} + \frac{p_0(1-p_0)}{n_0})} > z_{\alpha/2}$

Confidence intervals of the difference will be calculated according to the generally accepted Wald method:

$$(p_1 - p_2) \pm z_{\alpha/2}^* \sqrt{(\frac{p_1(1 - p_1)}{n_1} + \frac{p_2(1 - p_2)}{n_2})}$$

The number of patients for the portion taken from literature sources is taken from the 2020 publication and will be 82 [Parodi E, Russo G, Farruggia P, Notarangelo LD, Giraudo MT, Nardi M, et al. Management strategies for newly diagnosed immune thrombocytopenia in Italian AIEOP Centres: do we overtreat? Data from a multicentre, prospective cohort study. Blood Transfus. 2020;18(5):396.]

Methods of descriptive statistics (for categorical variables - number and part in %, for quantitative variables - n, arithmetic mean, median, standard deviation, minimum and maximum), including construction of graphs and charts, methods of interval estimation (calculate of 95% confidence intervals for proportions and differences of fractions).

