10.3.5. Significance level

The level of significance for the Shapiro-Wilk test is set at 0.01, and for other statistical tests at 0.05. In the case of the effect of multiple comparisons, the adjustment of the level of significance will be applied using the Holm method or the Benjamini-Hochberg method.

10.3.6. Work with missing or incomplete data.

Missing or incomplete data will be replaced using the Last-Observation-Carried-Forward (LOCF) method. Or by the method of enlarging the intervals for series where the transfer of the last measurement is not applicable.

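### Sections 5.3 and 10.4 disagree on whether follow-up dropouts count in the primary analysis, and no efficacy analysis in all dosed patients is planned

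*Combined protocol and SAP*

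**What the plan says.** Section 10.4 defines two sets. The all-dosed set, labelled ITT, holds everyone who received the drug at least once and is used for safety. The PP set is used for efficacy: "This population includes all patients who received protocol therapy in full, completed all scheduled visits, and had no significant protocol deviations". The synopsis makes the same split and says of PP: "The data obtained from this sample will be used for analysis based on efficacy criteria". Section 10.3.7 draws the non-inferiority conclusion from the primary variable and names no other population. No sensitivity analysis is described.

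Section 5.3 has its own rules. On incomplete courses it agrees with 10.4: "Patients who do not receive a full course of study drug are included in the safety analysis but not in the efficacy analysis". On patients who finish the infusions and leave later it does not: those who drop out in the follow-up "period are considered in the efficacy and safety analysis". It adds "The data of such patients are evaluated by parameters that can be analyzed at a certain point in time" and "The dropped data are not analyzed".

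Section 10.3.6 says: "Missing or incomplete data will be replaced using the Last-Observation-Carried-Forward (LOCF) method". It offers a widening of intervals where carrying forward does not fit.

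Section 10.1 says "For non-inferiority research, the null hypothesis is rejected if the conditions are met" and gives two criteria joined by an or: one treats the literature rate as fixed, the other adds the variance of the 82-patient reference. It then specifies a Wald interval with that reference, and 10.3.7 makes the 95% interval decisive. Section 8.1 requires response (R) to be confirmed by two blood tests at least 7 days apart, without bleeding.

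**The concern.** A patient who receives both infusions and leaves during follow-up is in the efficacy analysis under 5.3 and out of it under 10.4. The denominator of the one confirmatory test therefore cannot be read from the plan. In an open-label trial it could be settled after the results are known.

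The missing all-dosed analysis adds to this. There is one arm and an external reference of 78%, so no concurrent control shares any effect of selective loss. If leavers are mainly failures, the PP rate is too high, and nothing in the planned output would show it. The plan itself allows for 20% loss.

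**Working it through.** **Inputs.** Reference rate 0.78, reference size 82 and margin -0.25 (10.1, 10.2); z = 1.96 (two-sided 5%); 20% loss and 36 patients (10.2); 40 patients (4.1 and synopsis).

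**The plan's own figure.** (1.96 + 1.28)² × 0.78 × 0.22 / 0.25² = 28.82, rounded up to 29 as stated. 29/0.8 = 36.25, against the stated 36. Because 10.2 gives 36 and 4.1 gives 40, both are used below.

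**Decision limit.** L = p - 0.78 - 1.96 × sqrt(p(1-p)/n + 0.78 × 0.22/82), where the last term under the root is 0.00209. Non-inferiority is concluded if L > -0.25.

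**Case A: 40 dosed, one follow-up leaver with R already confirmed.**
- Section 5.3, 28/40: p = 0.700, standard error 0.0857, L = -0.080 - 0.168 = -0.248. Pass.
- Section 10.4, 27/39: p = 0.692, standard error 0.0869, L = -0.088 - 0.170 = -0.258. Fail.

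This case needs no assumption about coding a leaver as a failure, and PP is the stricter set.

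**Case B: 36 dosed, one follow-up leaver without confirmation, coded R = No under 5.3 (my assumption).**
- Section 10.4, 25/35: p = 0.714, standard error 0.0890, L = -0.066 - 0.174 = -0.240. Pass.
- Section 5.3, 25/36: p = 0.694, standard error 0.0894, L = -0.086 - 0.175 = -0.261. Fail.

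**How narrow these cases are.** Case B needs exactly 25 responders among 35 completers. The binomial probability is about 5% to 15% for assumed true rates of 0.60 to 0.78. At 40 dosed, an unconfirmed leaver coded No never changes the Wald result, because 28 responders are needed at both n = 39 and n = 40. If the reference is treated as fixed (the other 10.1 criterion), Case A does not flip (27/39 gives -0.2325, a pass). Case B then flips at 24 responders (24/35 gives -0.248, 24/36 gives -0.267).

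**Possible PP bias.** Take 36 dosed, a true all-dosed rate of 0.53 (0.78 - 0.25) and 20% attrition. Let f be the share of leavers who are failures. With random attrition the completer rate is (0.53 - 0.20(1-f))/0.80. With exactly 7 leavers it is (0.53 × 36 - 7(1-f))/29. Exact binomial probability of declaring non-inferiority (Wald):

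| Set | f | Random attrition | Exactly 7 leavers |
|---|---|---|---|
| All dosed (26/36 needed) | any | 1.5% | 1.5% |
| PP | 0.47 (unrelated to response) | 2.0% | 2.7% |
| PP | 0.50 | 2.4% | 3.2% |
| PP | 0.75 | 9.6% | 11.4% |
| PP | 1.00 | 26.7% | 29.5% |

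The documents do not give f, so this is a range and not an estimate.

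**When R can be confirmed.** The latest Day 7 count (Day 8, 192 h) minus the earliest 48-hour count (45 h) is 147 h, or 6.1 days, which is below 7. On scheduled counts, R can first be confirmed at visit 4. A patient who leaves before then has no confirmatory count unless an extra sample was taken, and the plan does not say how R is coded for such a patient.

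**The case against.** The best defence is that the examples sit on the boundary and partly rest on codings the plan does not contain. Section 5.3 evaluates leavers only on what can be analysed. An unconfirmed leaver could then be not evaluable for R, so both sections would give 25/35 and Case B disappears. That stands as a limit on Case B. It does not touch Case A, where the leaver is evaluable and the sections still differ.

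A reader might infer that PP favours the drug, or that the error rate is about 27%. The documents support neither. Case A runs the other way. The 27% needs 20% attrition, a true rate at the margin and every leaver failing; with half or fewer of the leavers failing, the inflation is negligible.

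A reader might also infer that LOCF flatly contradicts 5.3, or would manufacture confirmed responses. LOCF can apply to samples missed by patients who stay in the study (6.5.10 provides for missed samples), so the clash exists only if it is applied to leavers. Section 8.1 asks for blood tests, which a carried-forward value is not. What remains is that the plan does not rule it out.

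The synopsis and 4.3 class a steroid increase as ineffectiveness. Sections 5.3, 7.6, 10.4 and 11.2 could together be read as letting such a patient leave PP. No section says so: this is an ambiguity, not a contradiction.

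Finally, a reader might conclude that the all-dosed set must be primary. The documents do not say how the 82-patient source treated non-evaluable patients. If its 78% is an evaluable-patient rate, PP is closer to like for like.

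**Conclusion.** The point holds as a contradiction about the primary denominator and a missing analysis. Both can be read directly from 5.3, 10.4 and the synopsis, and neither depends on any calculation. Near the boundary, following one section or the other can change the conclusion in either direction: -24.8 against -25.8 points in Case A, and -24.0 against -26.1 in Case B if the leaver is coded R = No. Both examples use the Wald interval with the 82-patient reference. They show what is possible, not what is likely. The size and direction of any PP bias cannot be established from the documents.

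**What to change.** 1. Align 5.3, 10.4 and the synopsis on one rule for follow-up dropouts in the primary efficacy set, and fix it before database lock.
2. Pre-specify R and complete response (CR), with the same 95% interval, on the existing all-dosed set. Code R = No for an incomplete course or a missing confirmatory count. Report this at least as a sensitivity analysis beside PP, and explain any disagreement.
3. Require two observed platelet counts at least 7 days apart for R and CR. State that LOCF may not supply a confirmatory count, and make 10.3.6 consistent with 5.3.
4. Reconcile the synopsis, 4.3, 5.3, 7.6, 10.4 and 11.2 on how steroid increases and other prohibited therapy count in the endpoint and the analysis set. The sponsor decides which rule prevails.

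These changes need no new patients or data. The cost is a little more analysis and an all-dosed rate that may look less favourable.

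Whether the all-dosed set becomes primary is the sponsor's choice, and that step is not cheap. If completers respond at 78% and every leaver is coded No, the all-dosed rate is 0.78 × (1 - attrition). Wald power with 36 dosed is then 85%, 68%, 48% and 15% at 0%, 5%, 10% and 20% attrition (92%, 78%, 59% and 20% with 40). Requiring both sets to agree costs the same, because under that coding an all-dosed pass implies a PP pass. If the sponsor takes either route, the power in 10.2 must be restated.

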10.5. Representation of summary results

The results of the statistical analysis of the obtained results should be presented in the form of tables, which, if necessary, are illustrated with graphs and diagrams. Presentation of data should be structured, in accordance with the purpose and tasks of Study. It is necessary to clearly indicate the methods used, to characterize the array of data.

11. QUALITY CONTROL AND QUALITY ASSURANCE

11.1. Clinical trial monitoring

Regular visits of the study monitor on behalf of the sponsor and in accordance with standard operating procedures (SOPs), before, during and after the study contribute to the success of the study, and guarantee accurate data collection, timely detection of possible errors, documentation of clinical trials and ensuring the protection of the rights of clinical trial participants, compliance of the trial with the requirements of the legislation of Ukraine and Republic of Turkey.

Routine monitoring of the study includes:

- confirmation of the proper conduct and documentation of the process of obtaining informed consent, as well as screening and inclusion of participants in the study;
- verification of data in the IRF (eCRF) and primary medical records of study participants;
- confirmation of compliance with the requirements of the clinical center staff to perform diagnostic and therapeutic procedures of the study protocol;
- confirmation of documented deliveries, storage, distribution and disposal of the investigational medicinal product and clinical trial materials;
- confirmation of the competence of the staff of the clinical center, external laboratory, necessary for the study;
- confirmation of compliance of diagnostic and laboratory equipment with the requirements of safe and adequate use during the study;
- confirmation of the investigator's interaction with the local ethics committee on clinical trial safety and making amendments to the clinical trial protocol agreed with the sponsor.

Quality control of trial results is carried out by the Sponsor's staff / Sponsor's authorized representative (eg., CRO) who maintains an electronic survey database that identifies inconsistencies, erroneously entered data and omitted data.

If you have any questions or need clarification, the investigator is sent a special form by e-mail / fax, the request for which must be satisfied in writing within 7 days after delivery. In accordance with the requirements of the legislation, the sponsor or authorized state bodies have the right to inspect (audit) the logistics of the study and clinical trial documentation. The investigator must provide access to the documentation and all necessary information to the persons authorized to conduct the audit or inspection.

11.2. Amendments to the protocol, rejections, and violations of the protocol

The signatures of the investigators on the page of the protocol mean a written confirmation of consent to conduct study in accordance with this protocol. During the clinical study, changes and additions may be made to the study materials. Such changes and additions should be considered as amendments.

Amendments to clinical trial materials are considered significant if they may affect the objectives, forms of organization, methodology, statistical methods of processing the results of clinical trials. Amendments to the protocol should be kept together with the original version of the protocol. The number of the amendment and the date of its entry into force must be written on the title page of the protocol.

All deviations from the protocol during the study should be recorded during the monitoring of the clinical trial and reported to the Sponsor.

The investigator should not deviate from the protocol, except where it is necessary to exclude a serious risk to the health of patients in the study. If there are other unexpected circumstances that

| Bioven | Page 7 |
|----------------------------|-------------------------------|
| Trial Code: 2021-BV-ITP-BP | Version 1.4 from July 03, 202 |

require deviations from the protocol procedures, the investigator should consult the developer of the medicinal product or its representative (and the Ethics Committee, if necessary) to determine the appropriate procedure.

The study center must document all deviations from the protocol in the patient's original documentation. In the event of a significant deviation, the center should notify the developer of the medicinal product or its representative (and the Ethics Committee, if required). To do this, the investigator must fill out the form "Violation / deviation from the protocol" which is sent by fax to the clinical trial department of the company developing the drug. During the monitoring of the study center, the monitor of the clinical trial department may detect violations / deviations from the clinical trial protocol. In this case, he is responsible for notifying the investigators of the identified violations and for compiling the form "Violation / deviation from the protocol."

Violations/deviations from the protocol can be divided into gross (significant) and non-gross (minor). Examples of such deviations are given below.

Significant deviations from the protocol:

- unsigned/incorrectly signed informed consent of the patient to participate in a clinical trial;
- 2) violation/deviation from the criterion of patient selection;
- significant violation of the schedule of study procedures (deviation from the list of procedures provided by the protocol);
- significant violation/deviation from the schedule of treatment of patients (inconsistency of the therapy provided by the protocol, replacement of packaging of the study drug);
- 5) unreasonable disclosure of the patient's code and failure to notify the company conducting the study;
- failure to report (concealment of information) about a serious adverse event that occurred to the patient during the study;
- 7) non-compliance with the conditions of storage of the study drug.

Minor violations/deviations from the protocol:

- violation of the schedule of study procedures on the days of the visit, slightly exceeding the time frame provided by the protocol;
- 2) untimely (late) notification of SAE;
- 3) other unforeseen deviations.

Significant deviations include, but are not limited to, deviations that include forgery or improper study, increase the risk to the patient's health or distort the analysis of the main results of the study. All deviations from the protocol during the study should be recorded during the monitoring of the clinical trial and notification to the Sponsor.

